#### 4. Inclusion / Exclusion Criteria

The inclusion criteria include:

1. Adult patients  $\geq 18$  years old
2. Able to understand and sign a written informed consent form and willing to fulfil all study requirements
3. Healed edentulous ridge that is planned for an implant restoration.
4. Experimental site has not been previously augmented with xenograft
5. Experimental site has at least 2 mm of cancellous bone

The exclusion criteria include:

1. Uncontrolled systemic disease
2. Currently smoking  $>10$  cigarettes/day
3. History of head/neck radiotherapy within the past five years
4. Current use of oral bisphosphonates or history of IV bisphosphonate use
5. Pregnant, expecting to become pregnant, or lactating women
6. Presence of active periodontal disease
7. Poor oral hygiene
8. Previous history of implant failure at the site

[figure not shown]
The early termination criteria include:

1. The researcher believes that it is not in the patient's best interest to stay in the study

2. Based on the exclusion criteria, the patient becomes ineligible to participate
3. Patient's medical condition requires interventions which preclude involvement in the study (radiation therapy, chemotherapy, etc)
4. Patient does not follow study related instructions
5. The study is suspended or canceled

If subjects do not qualify or decide not to be part of this study, same treatments can be performed but without being part of this study. If subjects decide not to receive the treatments, consequences and probable outcomes will be explained.

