## 6. **Recruitment and Enrollment**

This investigation will be conducted at the University of Oklahoma, College of Dentistry, Department of Graduate Periodontics. Potential participants will be selected from the new and established patients of the College of Dentistry and will be contacted by the study coordinator by telephone for information regarding the participation in the study. Subjects that may qualify based on the inclusion and exclusion criteria will be scheduled for a screening examination appointment. Patient and the intervention site will be further evaluated at the screening appointment to confirm that patient qualifies to participate in the study.

Study personnel will provide each study candidate with a written informed consent form at the screening appointment at Graduate Periodontics clinic, prior to administration of any research related procedures. The protocol, procedures and objectives of the study and the patient's role in the study will be explained to each subject and/or legal guardian/authorized representative, before obtaining consent. Subjects will be given the opportunity to read the informed consent. Study personnel will answer all questions that the subject may have and ensure that the subject understood all aspects of the study. When the subject (or legal guardian/authorized representative) understands and is willing to (have the subject) participate in the clinical trial, he/she (or the legal guardian/authorized representative) must sign and date the Institutional Review Board (IRB) approved Informed Consent Form.

A translator will be provided for the participants that do not speak English. A witness that can speak both English and the patient's language will be present and will sign the Consent Form.

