## 7. **Risks and Benefits**

In preparation of the dental implant osteotomy, the osseodensification technique uses non-subtracting drills to compress the trabecular bone to periphery of the osteotomy site rather than removing it. As a result, there will be more bone available at the site for primary stability of the implant. This technique also expands the alveolar ridge and allows for placement of wider implants without the additional need for bone augmentation. By avoiding bone augmentation, this technique will not only be more cost effective, but also reduces treatment time and morbidity.

Animal studies and human case reports have reported significant ridge expansion, but there is a lack of randomized controlled clinical trial in humans. Because of this gap in knowledge, we do not know if the implants prepared with osseodensification technique, using the Densah® burs by Versah®, will be successful in the long term and if the expanded bone is retained or resorbed. A retrospective studyxi observed 92.8% survival rate of the implants and high implant stability quotient value 6 weeks after placement. Details about marginal bone loss or status of peri-implant health or inflammation were not reported. Based on the

available data, the risk of implant failure is low when using the Densah® burs by Versah® to create the osteotomy and the risk of adverse events is similar to conventional techniques. We would like to further investigate if peri-implant health is maintained in long-term.

As with any surgery, there are risks involved, some common risks include, but are not limited to:

- Swelling and/or bruising and discomfort in the surgical area.
- Possible damage to adjacent teeth.
- Possible damage to nerves which causes numbness or altered feeling in the teeth. In rare cases the numbness is permanent.

Complications that do occur are often minor and can be treated. Every possible effort will be made to minimize the risks involved.

For volumetric assessment of the peri-implant bone, we propose to take a series of CBCT. The radiographs will be limited to the area of the implants to reduce the radiation exposure. Lead apron with thyroid collar will be used to limit radiation exposure to radiosensitive organs.

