## 8. Statistical Methods

The biostatistics department at OUHSC will be utilized to review the data and perform statistical evaluation. Mean values, standard deviations, and medians will be calculated for clinical measurements. We will compare the bone volumetric changes before ridge expansion to different time points throughout healing. In addition, we will determine the implant survival and success rates by evaluating the probing pocket depth, bleeding index, gingival index, interproximal crestal bone level changes, biological and restorative complications of implants placed by the osseodensification technique. A fixed-effects regression model can account for correlations between repeated measures taken at each implant over time. This model can estimate a regression equation that describes the within-group changes.

Approximately 40 implants from patients seeking treatment at the University of Oklahoma, College of Dentistry will be recruited for this study. It is estimated that this sample size will provide 90% power of the test.

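### Section 8 gives no patient count and no provision for several implants in one patient; if patients contribute several with correlated changes, precision will be overstated

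*Combined protocol and SAP*

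**What the plan says.** Section 8 (Statistical Methods) sets the sample in implants: "Approximately 40 implants from patients seeking treatment at the University of Oklahoma, College of Dentistry will be recruited for this study". No section gives a number of patients, a maximum number of implants per patient, or a rule of one study implant per patient.

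The single model named is described by the correlation it handles: "A fixed-effects regression model can account for correlations between repeated measures taken at each implant over time". Its stated target is change within the group. Section 8 mentions no patient-level term, patient-clustered variance or GEE. Survival and success rates are to be determined, but no interval or test for them is described.

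On power the section says only "It is estimated that this sample size will provide 90% power of the test". It does not name the endpoint, test, alpha, effect or SD, or say whether clustering was allowed for.

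Elsewhere the site is mostly in the singular. Section 4 requires a "Healed edentulous ridge that is planned for an implant restoration", and Section 6 says "Patient and the intervention site will be further evaluated at the screening appointment". Section 7, describing the limited CBCT field, speaks of implants in the plural. None of this is a rule either way.

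**The concern.** The primary aim in Section 1 concerns change: gain in bone volume and density at placement, and retention through osseointegration and loading. Fixed effects for implants remove stable differences in level between implants, and therefore between patients. They do not remove correlation between the changes at two implants in the same mouth.

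The protocol itself allows for shared causes of change. Patients smoking up to 10 cigarettes a day are eligible, so smoking can differ between patients. The restorative dentist is the patient's choice (Section 3), so restorative complications can run together within a patient. Early termination applies to the patient, so all of that patient's implants leave together.

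If the model is followed as described and some patients have several implants, correlated changes would be analysed as independent. Tests would reject too often, and intervals would claim more information than the patients provide.

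**Working it through.** **Inputs from the documents.** About 40 implants and 90% power (Section 8); background expansion of 1.8 ± 1.1 mm at the crest and 0.9 ± 0.8 mm at the 10 mm mark, from a retrospective study of 28 implants (Section 2); background implant survival of 92.8% (Section 7).

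**Assumptions, because the documents are silent.** Two-sided alpha 0.05; m implants per patient; ICC = correlation of change between implants in one patient.

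**1. The plan's own power figure.** It cannot be reproduced or refuted, because its inputs are missing. With 40 independent implants and a paired test, 90% power corresponds to a standardized change of (1.960 + 1.282)/√40 = 0.51 (0.53 by noncentral t). The background figures do not lead to 40: 1.8/1.1 needs 7 implants and 0.9/0.8 needs 11 by paired t.

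**2. Effect of clustering.** Design effect DE = 1 + (m − 1) × ICC; effective n = 40/DE; true SE = naive SE × √DE; true type I error = 2 × [1 − Φ(1.96/√DE)]; power of a correctly sized test = Φ(3.2415/√DE − 1.96).

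| m | ICC | DE | Effective n | SE ratio | Type I error | Power |
|---|---|---|---|---|---|---|
| 1 | any | 1.00 | 40.0 | 1.00 | 5.0% | 90% |
| 2 | 0 | 1.00 | 40.0 | 1.00 | 5.0% | 90% |
| 2 | 0.1 | 1.10 | 36.4 | 1.05 | 6.2% | 87% |
| 2 | 0.3 | 1.30 | 30.8 | 1.14 | 8.6% | 81% |
| 2 | 0.5 | 1.50 | 26.7 | 1.22 | 11.0% | 75% |
| 4 | 0.3 | 1.90 | 21.1 | 1.38 | 15.5% | 65% |

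For unequal numbers per patient, m should be size-weighted. If 40 implants come from 32 patients as evenly as possible (24 with one, 8 with two), m = (24 × 1 + 8 × 4)/40 = 1.4, and at ICC 0.3 DE = 1 + 0.4 × 0.3 = 1.12.

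**3. Simulation check** (20,000 trials per setting, 40 implants, two per patient, naive test of mean within-implant change). A patient effect on baseline level alone gives a type I error of 4.8%, because it cancels in the change. A patient effect on change with ICC 0.1, 0.3 and 0.5 gives 6.3%, 8.8% and 10.8%, in line with the formula.

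**4. Would the expansion conclusion change?** If the background figures applied to 40 implants, naive z = 1.8/(1.1/√40) = 10.3 and 0.9/(0.8/√40) = 7.1. At DE 1.50 these become 10.3/1.22 = 8.4 and 7.1/1.22 = 5.8. Both remain far above 1.96.

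**5. Survival, if an interval were reported.** Assuming 37 of 40 implants survive (92.5%, close to the background rate), the Clopper-Pearson interval is 79.6% to 98.4%. Recomputed at n = 40/DE it is 77.1% to 98.9% for DE 1.3, and 75.4% to 99.1% for DE 1.5.

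**The case against.** The strongest reply is that both conditions are unproven. The documents never say that a patient may have more than one study implant, mostly refer to one site, and give no within-patient correlation. With one implant per patient there is nothing to correct. This stands: a reader might infer that the reported standard errors are bound to be too small, and the documents do not support that. They do leave the possibility open, since the sample is counted in implants without a patient number or a limit.

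Second, Section 8 says what a model can do and leaves the analysis to the biostatistics department. A patient term is absent, not excluded. That is fair, but a patient term is also not promised, and choosing the unit of analysis after seeing the data is hard to defend.

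Third, no survival interval is planned. A reader might infer that the plan contains a faulty one; it contains none. The point therefore applies only to an interval that is eventually reported. Ignoring clustering in the variance does not make the survival proportion itself wrong.

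Fourth, this is a single-arm case series with a large expected immediate effect. Step 4 of the working supports this, and it limits the seriousness. It does not cover retention, density, ISQ or crestal bone change, where contrasts may be smaller and no background effect sizes are given.

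**Conclusion.** The omission is certain: no patient count, no limit on implants per patient, and no provision for correlation between implants in one patient. The consequence is conditional on some patients contributing several implants and on positive correlation of their changes.

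If patients average two implants, an ICC of change of 0.1 to 0.5 puts a nominal 5% test at about 6% to 11%. Power falls to between 87% and 75%, provided the stated 90% rests on 40 independent implants. With one implant per patient or an ICC of 0, both effects vanish.

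It would go too far to conclude that the 90% figure is wrong, since it cannot be checked, or that the immediate-expansion finding is unsafe. What is exposed is inference on smaller contrasts such as retention, and the width of every interval. This should be fixed because the remedy is cheap, but it does not undermine the study.

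**What to change.** In Section 8:

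1. State the expected number of patients and the expected and maximum implants per patient, and report both at the end. If only one study implant per patient is analysed, say so; nothing further is then needed.
2. Otherwise, estimate changes from implant-level repeated measures with standard errors clustered on patient and a small-sample correction (t reference, patients minus 1 degrees of freedom). With equal numbers per patient, for a simple mean change, this is a one-sample t-test on patient means. A mixed model is an alternative, provided it includes a patient-level random effect on change. A patient intercept alone is not enough, because it cancels in the within-implant change.
3. For any survival or complication interval, use a method that allows for clustering and still works with few or no failures, for example an exact or Wilson interval at the design-effect-adjusted sample size, with the design effect fixed in advance. Reporting the patient-level proportion as well is another option. A patient bootstrap or logistic GEE is a poor choice here: at 92.8% survival the chance of no failure in 40 independent implants is 0.928^40, about 5%, and both methods break down in that case.
4. Say whether the power statement treats the 40 implants as independent.

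The cost is a few sentences and a small change to the analysis code, with somewhat wider intervals. With 20 patients, the reduced degrees of freedom alone would lower 90% power to about 88% even at ICC 0.

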## 9. Data and Safety Monitoring Plan

The investigators will periodically audit the study records of each participant to evaluate the progress of the study, verify its accuracy and completeness, and resolve any inconsistencies in the study records. The Principal Investigator may stop the study if it is observed that the protocol or sound clinical practices are not being followed. The Principal Investigator may exclude subjects from the study if review of their records indicates violations of the protocol or if there are other reasons to believe that their inclusion would jeopardize the validity of the study. Subjects discontinued due to adverse events will not be replaced.

The investigator will make an accurate and adequate written progress reports to the IRB at appropriate intervals, not exceeding one year, and a final report to the IRB within 3 months after completion or termination of the study. The investigator will make an accurate and adequate special report to the IRB on any serious, unexpected, or life-threatening adverse

event or death occurring in relationship to the study whether regarded as study-related or not.

Any adverse event, including both observed or volunteered problems, complaints, or symptoms, are to be recorded as mild, moderate or severe as follows:

- MILD: events are usual transient, requiring no special treatment, and do not interfere with the subject's daily activities.
- MODERATE: events traditionally introduce a low level of inconvenience of concern to the subject and may interfere with daily activities, but are usually ameliorated by simple therapeutic measures.
- SEVERE: events interrupt a subject's usual daily activity and traditionally require systemic drug therapy or other treatment.

When intensity changes occur more frequently than once a day, the maximum intensity for the event should be listed. If the intensity category changes over a number of days, then these changes should be recorded separately (i.e. having distinct onset days).

The investigator will determine the relationship of the adverse event to the study test material. One of the following determinations will then be used to document the relationship of the adverse event to the study test material:

- NOT RELATED
- POSSIBLE
- PROBABLE

## 10. **Confidentiality**

Patient information is kept within the University of Oklahoma. Paper records will be maintained in a locked fireproof storage room and electronic records will be stored on an encrypted hard drive, which meets the University IT Security requirements. Patient records will be protected by the Health System's privacy policies and according to the privacy regulations of the federal Health Insurance Portability and Accountability Act of 1996 (HIPAA).

These records will be available to copying and inspection if requested by a properly authorized employee of the Department of Health and Human Services, under the supervision of the investigator or a designated representative and in accordance with federal regulations.

The investigators understand that the office and hospital records of subjects entered in this study will be required to be available under the supervision of the investigator or a designated representative for inspection by the FDA. All subject related information provided to the FDA will be done so without subject names or other identifying information.

